**Table 5: Efficacy Results in Patients with Classical HL Post-auto-HSCT Consolidation (Study 3)**

Progression-free Survival	ADCETRIS N=165	Placebo N=164
Independent Review Facility		
Number of events (%)	60 (36)	75 (46)
Median months (95% CI)	42.9+ (30.4, 42.9+)	24.1 (11.5, NE * )
Stratified Hazard Ratio (95% CI)	0.57 (0.40, 0.81)	
Stratified Log-Rank Test P-value		P=0.001

\* Not estimable

+ Estimates are unreliable

**Figure 1: Kaplan-Meier Curve of IRF-Assessed Progression-Free Survival (Study 3)**

BV: Brentuximab Vedotin; BSC: Best Supportive Care

## 14.2 Systemic Anaplastic Large Cell Lymphoma

### *Clinical Trial in Relapsed sALCL (Study 2)*

The efficacy of ADCETRIS in patients with relapsed sALCL was evaluated in one open-label, single-arm, multicenter trial. This trial included patients who had sALCL that was relapsed after prior therapy. Fifty-eight patients were treated with 1.8 mg/kg of ADCETRIS administered intravenously over 30 minutes every 3 weeks. An IRF performed efficacy evaluations which included overall response rate (ORR = complete remission [CR] + partial remission [PR]) and duration of response as defined by clinical and radiographic measures including computed tomography (CT) and positron-emission tomography (PET) as defined in the 2007 Revised Response Criteria for Malignant Lymphoma (modified).

The 58 patients ranged in age from 14–76 years (median, 52 years) and most were male (57%) and white (83%). Patients had received a median of 2 prior therapies; 26% of patients had received prior autologous hematopoietic stem cell transplantation. Fifty percent (50%) of patients were relapsed and 50% of patients were refractory to their most recent prior therapy. Seventy-two percent (72%) were anaplastic lymphoma kinase (ALK)-negative.

The efficacy results are summarized in Table 6. Duration of response is calculated from date of first response to date of progression or data cutoff date.

**Table 6: Efficacy Results in Patients with Systemic Anaplastic Large Cell Lymphoma (Study 2)**

	N=58		
	Percent (95% CI)	Duration of Response, in months	
		Median (95% CI)	Range
CR	57 (44, 70)	13.2 (10.8, NE*)	0.7 to 15.9+
PR	29 (18, 41)	2.1 (1.3, 5.7)	0.1 to 15.8+
ORR	86 (77, 95)	12.6 (5.7, NE*)	0.1 to 15.9+

\*Not estimable

+ Follow up was ongoing at the time of data submission.

## 16 HOW SUPPLIED/STORAGE AND HANDLING

### 16.1 How Supplied

ADCETRIS (brentuximab vedotin) for Injection is supplied as a sterile, white to off-white preservative-free lyophilized cake or powder in individually-boxed single-use vials:

- NDC (51144-050-01), 50 mg brentuximab vedotin.

### 16.2 Storage

Store vial at 2–8°C (36–46°F) in the original carton to protect from light.

### 16.3 Special Handling

ADCETRIS is an antineoplastic product. Follow special handling and disposal procedures.

## 17 PATIENT COUNSELING INFORMATION

- Peripheral neuropathy

Advise patients that ADCETRIS can cause a peripheral neuropathy. They should be advised to report to their health care provider any numbness or tingling of the hands or feet or any muscle weakness [see *Warnings and Precautions* (5.1)].

- Fever/Neutropenia

Advise patients to contact their health care provider if a fever of 100.5°F or greater or other evidence of potential infection such as chills, cough, or pain on urination develops [see *Warnings and Precautions* (5.3)].

- Infusion reactions

Advise patients to contact their health care provider if they experience signs and symptoms of infusion reactions including fever, chills, rash, or breathing problems within 24 hours of infusion [see *Warnings and Precautions* (5.2)].

- Hepatotoxicity

Advise patients to report symptoms that may indicate liver injury, including fatigue, anorexia, right upper abdominal discomfort, dark urine, or jaundice [see *Warnings and Precautions (5.8)*].

- Progressive multifocal leukoencephalopathy

Instruct patients receiving ADCETRIS to immediately report if they have any of the following neurological, cognitive, or behavioral signs and symptoms or if anyone close to them notices these signs and symptoms [see *Boxed Warning, Warnings and Precautions (5.9)*]:

- changes in mood or usual behavior
- confusion, thinking problems, loss of memory
- changes in vision, speech, or walking
- decreased strength or weakness on one side of the body

- Pulmonary Toxicity

Instruct patients to report symptoms that may indicate pulmonary toxicity, including cough or shortness of breath [see *Warnings and Precautions (5.10)*].

- Pancreatitis

Advise patients to contact their health care provider if they develop severe abdominal pain [see *Adverse Reactions (6.2)*].

- Gastrointestinal Complications

Advise patients to contact their health care provider if they develop severe abdominal pain, chills, fever, nausea, vomiting, or diarrhea [see *Warnings and Precautions (5.12)*].

- Females and Males of Reproductive Potential

ADCETRIS can cause fetal harm. Advise women receiving ADCETRIS to avoid pregnancy during ADCETRIS treatment and for at least 6 months after the final dose of ADCETRIS.

Advise males with female sexual partners of reproductive potential to use effective contraception during ADCETRIS treatment and for at least 6 months after the final dose of ADCETRIS [see *Use in Specific Populations (8.3)*].

Advise patients to report pregnancy immediately [see *Warnings and Precautions (5.13)*].

- Lactation

Advise patients to avoid breastfeeding while receiving ADCETRIS [see *Use in Specific Populations (8.2)*].

Manufactured by:  
Seattle Genetics, Inc.

[name]  
[name]  
U.S. License 1853

ADCETRIS, Seattle Genetics and  are US registered trademarks of Seattle Genetics, Inc.

*ADCETRIS® (brentuximab vedotin)*

26

1. INTRODUCTION

This document describes the rules and conventions to be used in the presentation of safety, pharmacokinetic, pharmacodynamic and efficacy data for Protocol SGN35-022. It describes the data analysis to be conducted after data base lock and unblinding, and is to be signed prior to those milestones.

This statistical analysis plan (SAP) is based on protocol Amendment 2, dated 25 July 2016.

2. STUDY OBJECTIVES

2.1. PRIMARY OBJECTIVE

To evaluate the safety and tolerability of brentuximab vedotin in adults with active systemic lupus erythematosus (SLE).

2.2. SECONDARY OBJECTIVES

The secondary objectives of the study are:

- to explore the pharmacokinetics (PK) and pharmacodynamics (PD) of brentuximab vedotin in adults with active SLE; and
- to explore the efficacy of brentuximab vedotin in adults with active SLE.

3. STUDY DESIGN

3.1. GENERAL DESCRIPTION

This is a multicenter, randomized, placebo-controlled, double-blind, multiple-ascending-dose study to evaluate the safety and tolerability of brentuximab vedotin in subjects with active SLE. Approximately 40 subjects in 4 dosing cohorts (10 subjects per cohort) are planned for study participation at approximately 20 study sites in the US. Subjects who meet inclusion and exclusion criteria will be randomly assigned in a 4:1 ratio within each dosing cohort to receive IV brentuximab vedotin or placebo every 3 weeks (Days 1, 22, 43, and 64) for a total of 4 doses. The following doses are planned for each ascending dose cohort:

- 0.3 mg/kg IV every 3 weeks for 4 doses;
- 0.6 mg/kg IV every 3 weeks for 4 doses;

Document: SGN35-022 SAP v1 V0.3
Author: [REDACTED]

Version Number: 1.0
Version Date: 31Jan2017

Template No: CS_TP_BS016 – Revision 3
Effective Date: 01Apr2016

Reference: CS_WI_BS005

[REDACTED]

- 1.2 mg/kg IV every 3 weeks for 4 doses; and
- 1.8 mg/kg IV every 3 weeks for 4 doses.

Individual doses are based on subject weight and will be administered as an IV infusion over approximately 30 minutes. Dose and/or schedule adjustments are not permitted. In-line filters are permitted. However the study drug cannot be mixed with other medications. Further instructions on the dose preparation and administration will be provided in the Pharmacy Manual.

Initiation of enrollment at the next dose level will only commence upon endorsement of the SMC following review of the safety data. Depending on the findings, the SMC may recommend additional enrollment of subjects at specific dose levels to better characterize the safety of a particular dose, or may recommend different dose regimens based on the emerging safety data. When available from each full cohort, the SMC will review all Day 85 safety data and may recommend that an already enrolled succeeding dose cohort be discontinued, or its treatment regimen truncated. Doses are not to exceed 1.8 mg/kg IV every 3 weeks or equivalent. Up to 20 subjects total may be enrolled via additional SMC-recommended cohorts for a total of up to 60 subjects.

3.1.1. SAMPLE SIZE

Since no prior studies in SLE have been conducted with brentuximab vedotin, the primary objective of this study is to evaluate the safety and tolerability of brentuximab vedotin in this patient population. As such, the number of subjects planned has been based on clinical judgment, to provide sufficient experience upon which to design a larger efficacy (Phase 2) study.

3.1.2. BLINDING

This is a randomized, double-blind, placebo-controlled study with limited access to the randomization code. Brentuximab vedotin and placebo solutions for IV administration will be identical in physical appearance. The treatment each subject will receive during the treatment period will not be disclosed to the Investigator, study site personnel, subject, or the blinded study team.

For more details on blinding refer section 5.6 Blinding of the protocol.

3.2. METHOD OF TREATMENT ASSIGNMENT

The subjects will be randomly assigned to the study treatment by the study site using Interactive Web Response System (IWRS). The IWRS will provide the study drug kit number(s) of the blinded study drug to be dispensed. Randomization will occur on Day 1 prior to the first dose.

3.3. SCHEDULE OF EVENTS

Schedule of events can be found in APPENDIX 2: SCHEDULE OF EVENTS of the protocol.

Document: SGN35-022 SAP v1 V0.3
Author: [REDACTED]

Version Number: 1.0
Version Date: 31Jan2017

Template No: CS_TP_BS016 – Revision 3
Effective Date: 01Apr2016

Reference: CS_WI_BS005

[REDACTED]

3.4. CHANGES TO ANALYSIS FROM PROTOCOL

There are no meaningful deviations from the analyses planned in the study protocol.

4. PLANNED ANALYSES

4.1. SAFETY MONITORING COMMITTEE (SMC)

Please refer to the SMC SAP.

4.2. INTERIM ANALYSIS

No formal interim analyses are planned.

4.3. FINAL ANALYSIS

The final analyses will be conducted after the finalization of the SAP, database lock and unblinding.

5. ANALYSIS SETS

5.1. SAFETY ANALYSIS SET

The safety analysis set (SAF) includes all subjects who receive at least one dose of study medication. Subjects in this population is used for all safety, dosing, demographic, disposition and pharmacodynamic summaries. The SAF will be analyzed according to the treatment administered.

5.2. FULL ANALYSIS SET

The full analysis set (FAS) includes all randomized subjects, without regard for treatment administration. The FAS will be analyzed according to the treatment assigned, and used for all efficacy analyses.

5.3. PER-PROTOCOL ANALYSIS SET

The per-protocol analysis set (PPAS) includes all randomized subjects who have received at least 1 dose of study medication, have both the baseline and Day 85 SRI and have no protocol violations. The PPAS will be analyzed according to the actual treatment received, and will be used for the secondary efficacy analysis only.

Document: SGN35-022 SAP v1 V0.3
Author: [REDACTED]

Version Number: 1.0
Version Date: 31Jan2017

Template No: CS_TP_BS016 – Revision 3
Effective Date: 01Apr2016

Reference: CS_WI_BS005

[REDACTED]

5.4. PHARMACOKINETIC ANALYSIS SET

The PK analysis set (PKAS) includes all randomized subjects who have received at least 1 dose of brentuximab vedotin, have a post-baseline PK measurement. The PKAS will be analyzed according to the treatment administered.

5.5. PHARMACODYNAMIC ANALYSIS SET

The PD analysis set (PDAS) includes all randomized subjects who have received at least 1 dose of study medication, have a post-baseline PD measurement. The PDAS will be analyzed according to the treatment administered.

6. GENERAL CONSIDERATIONS

Some minor modifications may be necessary to the planned design of tables, figures, and listings to accommodate data collected during the actual study conduct.

6.1. SUMMARY STATISTICS

For qualitative variables, the population size (N for sample size and n for available data) and the percentage (of available data) for each class of the variable will be presented. Quantitative variables will be summarized using descriptive statistics, including N, mean, standard deviation (SD), coefficient of variation (CV%), median, 25th percentile, 75th percentile, minimum, and maximum values. CV will not be presented for change from baseline results. 95% CI will be reported in place of CV for efficacy variables.

In general, data will be summarized for each dose group, with all placebo subjects aggregated into a single group, and scheduled study day/visit. Data for all active-treated subjects combined will also be presented when appropriate. Descriptive statistics for optional tests will be suppressed if the sample size is below 3.

6.2. PRECISION

All variables, including derivations thereof, will be reported to the same precision as the source data.

For the reporting of descriptive statistics, the mean, standard deviation, standard error and confidence intervals will be presented to one digit more precision than the source data. The minimum, median, 25th percentile, 75th percentile and maximum will be presented to the same precision as the source data. Coefficient of variation will always be reported to 1 decimal place. P-values, if any, shall be reported to four decimal places or as <0.0001.

6.3. BASELINE

Baseline, is defined as the last scheduled non-missing measurement taken prior to dosing and will correspond to

Document: SGN35-022 SAP v1 V0.3
Author: [REDACTED]

Version Number: 1.0
Version Date: 31Jan2017

Template No: CS_TP_BS016 – Revision 3
Effective Date: 01Apr2016

Reference: CS_WI_BS005

[REDACTED]

Day 1 (predose) for clinical laboratory evaluations, physical examinations, vital signs and ECGs. Baseline for efficacy and pharmacodynamics is defined as the Day 1 assessments. However, if a subject is missing the planned baseline collection, the previous non-missing evaluation if available will become the baseline value.

End of treatment (EOT) is defined as Day 85 for use in the efficacy analyses.

6.4. RETESTS, UNSCHEDULED VISITS AND EARLY TERMINATION DATA

Unscheduled measurements will not be included in summary statistics, but will contribute to the assessment of clinical outliers. Early termination results will be recorded as such, and included with the summaries.

In the case of a retest of a scheduled assessment, the earliest available measurement for that scheduled time (i.e. the original assessment) will be used for summaries unless flagged as invalid.

Listings will include all scheduled, unscheduled, retest and early discontinuation data.

6.5. COMMON CALCULATIONS

- Change from baseline (CFB) = Observed Value (after baseline) – Baseline Value
- Percent change from baseline (PCFB) = CFB / Baseline Value * 100.
- Change from end of treatment (CFEOT) = Observed Value (after treatment end) – EOT Value
- Percent change from end of treatment (PCFEOT) = CFEOT / EOT Value *100.

6.6. SOFTWARE VERSIONS

All derivations, statistical analyses, summaries and listings will be generated using SAS version 9.4 or higher (SAS Institute, Inc., Cary, North Carolina). Graphics may be prepared using the same version of SAS.

7. STATISTICAL CONSIDERATIONS

7.1. ADJUSTMENT FOR COVARIATES

The baseline value for a dependent variable will be used as a continuous covariate in statistical models when available.

7.2. MULTICENTER STUDIES

Given the small number of subjects per study center/site, no adjustment for site effects will be considered OR sites will be aggregated according to geographic regions: USA (Western, Southern, Central, Northeast), Central America, South America, and Canada.

Document: SGN35-022 SAP v1 V0.3
Author: [REDACTED]

Version Number: 1.0
Version Date: 31Jan2017

Template No: CS_TP_BS016 – Revision 3
Effective Date: 01Apr2016

Reference: CS_WI_BS005

7.3. MISSING DATA

Missing data will not be imputed. Treatment attribution of adverse events and concomitant medications, in the event of missing dates, will be determined as specified in Appendix 2.

7.4. MULTIPLICITY

Given the lack of primary statistical hypotheses, small sample size, large number of endpoints, and the hypothesis generating nature of this study, no adjustment for multiplicity will be made for this study.

7.5. SUBGROUP ANALYSES

No subgroup analyses will be performed for this study.

8. OUTPUT PRESENTATIONS

Appendix 1 shows conventions for presentation of data in outputs.

The templates provided with this SAP outline the presentations, format and content of the summary tables, figures and listings to be provided by Quintiles Biostatistics.

9. DISPOSITION AND WITHDRAWALS

All subjects who provide informed consent, are randomized and received study medication, will be accounted in this study. Subject disposition will be tabulated for each dose group with the number of subjects who are randomly assigned to treatment, complete the study, prematurely discontinue, and the reason for early discontinuation. A listing will present dates of completion or early withdrawal and the reason for early discontinuation, if applicable, for each subject.

Listings of subject consent, screen failures, inclusion/exclusion criteria responses, study eligibility, study drug administration and study visits will be provided.

10. DEMOGRAPHIC AND OTHER BASELINE CHARACTERISTICS

Demographic characteristics such as age, sex, race, ethnicity, height, weight, and body mass index (BMI) will be summarized and tabulated by dose group. Descriptive statistics will be presented for age, height, weight, and BMI. Frequency counts and percent will be presented for sex, race, and ethnicity. No statistical testing will be carried out for demographic or other baseline characteristics.

10.1. DERIVATIONS

- BMI (kg/ m²) = weight (kg)/ height (m)²
- Age (years) will be calculated as the number of complete years for patients' birth date relative to date of consent.

10.2. LUPUS DIAGNOSIS

Current signs and symptoms for lupus will be listed along with the date and length of lupus diagnosis.

10.3. CHEST X-RAY

The date and overall interpretation of chest x-rays taken in the 3-months prior to Screening will be listed.

11. PROTOCOL DEVIATIONS AND VIOLATIONS

A protocol deviation is any noncompliance with the clinical trial protocol, GCP, or Manual of Procedure requirements. The noncompliance may be either on the part of the subject, the site PI, or the study site staff. Any subject enrolled who does not meet eligibility criteria will be considered an enrollment deviation.

All protocol deviations will be summarized with the number (%) of subjects by category and/or type deviation.

Protocol violations are defined as those meriting exclusion from the PPAS. These will be identified through review of the protocol deviation logs prior to database lock and unblinding. All protocol violations and those meriting exclusion from the PPAS will be listed.

12. MEDICAL HISTORY

Medical History is collected and will be coded using MedDRA Version 18.0. Medical history will be listed and summarized by SOC and preferred term for each treatment group.

13. MEDICATIONS

Medication usage is collected and coded using the WHO Drug Dictionary 01MAR2014.

- 'Prior' medications are medications which started and stopped prior to providing informed consent.
- 'Concomitant' medications are medications which were taken during the treatment period, or specifically:
 - started after providing informed consent or
 - started prior to providing informed consent and ended after providing informed consent or was ongoing

Document: SGN35-022 SAP v1 V0.3
Author: [REDACTED]

Version Number: 1.0
Version Date: 31Jan2017

Template No: CS_TP_BS016 – Revision 3
Effective Date: 01Apr2016

Reference: CS_WI_BS005

[REDACTED]

See Appendix 2 for handling of partial dates for medications, in the case where it is not possible to define a medication as prior, concomitant, or post treatment, the medication will be classified by the worst case; i.e. concomitant.

A subject listing of all previous and concomitant medications will be presented. The total number and percentage of subjects with concomitant medications will be presented by Anatomical Therapeutic Chemical (ATC) classification and preferred term. This summary will not include previous medication.

Lupus specific medications will be listed separately, based on the specific eCRF panel.

14. STUDY MEDICATION EXPOSURE

Exposure to study medication as the number of doses administered (1, 2, 3 or 4) will be listed for each subject, and summarized.

The percentage of subjects with dose interruptions due to treatment-emergent AEs will be summarized by treatment.

15. EFFICACY OUTCOMES

There is no primary efficacy endpoint defined for this study. Secondary and exploratory efficacy analysis are described below.

15.1. GENERAL METHODOLOGY

If subjects are missing assessments during participation in the trial (prior to completion or withdrawal), these will be assumed to be non-events. The denominator used for percentages or proportions in tabulations will be the number of subjects in the analysis set with available data for the corresponding time point and treatment group.

The time to a pre-defined event will be calculated in days for each subject and response/flare as the date of the first event minus the date of randomization. If the date of the event is not recorded, the date of the study visit will be used. When there are multiple criteria to be met, the first event date is defined as the first date on which all criteria are met concurrently. If no flare/event occurred prior to the end of study participation (including for early termination), the time to flare will be regarded as censored at termination.

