#### **4.4.4 Subject Withdrawal**

All subjects are free to withdraw from participation in the study at any time, for any reason, specified or unspecified, and without prejudice to further treatment. The criteria for enrollment are to be followed explicitly. If a subject who does not meet enrollment criteria is inadvertently enrolled, that subject should be withdrawn from the study, and the Sponsor and Quintiles must be contacted.

In addition, subjects will be withdrawn from study drug and from the study in the following circumstances:

- The Investigator decides that the subject should be withdrawn. If this decision is made because of an intolerable AE or a clinically significant laboratory value, the study drug is to be discontinued and appropriate measures are to be taken. The Sponsor and Quintiles are to be notified immediately.
- The subject experiences a clinically significant worsening of SLE warranting a significant change in therapy according to the Investigator. The Sponsor and Quintiles are to be notified immediately.
- The subject experiences signs or symptoms suggestive of PML.
- The subject experiences any Grade 3 or higher infection.
- The subject experiences any Grade 3 (according to the National Cancer Institute's Common Terminology Criteria for Adverse Events [NCI-CTCAE]) or higher neutropenia (ie, absolute neutrophil count  $< 1.0 \times 10^9/L$ ), thrombocytopenia (ie, platelet count

$< 50 \times 10^9/L$ ), anemia (ie, hemoglobin  $< 8.0 \text{ g/dL}$  or transfusion indicated), or liver function test abnormal (ie, ALT or AST  $> 5x \text{ ULN}$ ) that does not correct to Grade 1 or better before the next scheduled dose of brentuximab vedotin.

- The subject experiences any Grade 3 or higher neuropathy. Dosing will be withheld for any subject who experiences Grade 2 neuropathy, but decisions to resume dosing will be made on a case-by-case basis in consultation with the Medical Monitor (see Section 5.1).
- The subject has missed more than 1 dose.
- The subject is unwilling to continue in the study.
- The subject exhibits a lack of compliance with protocol.
- The Investigator or the Sponsor, for any reason, stops the study.

Subjects who discontinue the study early will have early termination procedures performed as shown in the schedule of events (Table 3). Subjects who are withdrawn from the study will not be replaced.

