### 8.2 Statistical Methods

Data will be analyzed by Quintiles Inc. biostatistical staff. All details regarding the statistical analysis and the preparation of tables, listings, and figures will be described in the Statistical Analysis Plan prepared by Quintiles and approved by the Sponsor before database lock.

Summaries for safety and efficacy data collected will be presented for each treatment group, ie, for brentuximab vedotin 0.3, 0.6, 1.2, or 1.8 mg/kg IV every 3 weeks and placebo at each scheduled visit/assessment. Placebo subjects across cohorts will be aggregated for analysis. Subjects will be evaluated according to the treatment received.

For qualitative parameters, the population size (N for sample size and n for available data) and the percentage (of available data) for each class of parameters will be presented. Quantitative parameters will be summarized by the population size (N for sample size and n for available data), the mean, the standard deviation, the median, 25th percentile, 75th percentile, the minimum, and the maximum values. Geometric means and coefficients of variation will be included as deemed relevant.

A nominal significance level of 5% will be used for exploratory inference testing.

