### **8.2.2 Missing Data**

No imputation will be performed on any missing assessments.

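### The available-data denominator in SAP 15.1 drops subjects withdrawn before Day 85 from the FAS SRI rate, and the rules for missed visits contradict each other (minor)

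*SAP*

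**What the plan says.** **Denominator.** SAP 15.1 (General Methodology): "The denominator used for percentages or proportions in tabulations will be the number of subjects in the analysis set with available data" at the time point, by treatment group. This follows the general rule for percentages in protocol 8.2 ("the percentage (of available data) for each class of parameters will be presented") and SAP 6.1 ("the percentage (of available data) for each class of the variable will be presented").

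**Missing assessments.** The preceding text of SAP 15.1 reads: "If subjects are missing assessments during participation in the trial (prior to completion or withdrawal), these will be assumed to be non-events". SAP 7.3 says "Missing data will not be imputed" and protocol 8.2.2 says "No imputation will be performed on any missing assessments". SAP 15.3.7.1 leaves an ACR response missing when too few components are available. SAP 3.4 declares no meaningful deviation from the protocol's analyses.

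**Analysis sets.** The FAS is all randomized subjects and serves all efficacy analyses (SAP 5.2). The per-protocol set requires a baseline and a Day 85 SRI (SAP 5.3).

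**Withdrawal.** Protocol 4.4.4 states that "subjects will be withdrawn from study drug and from the study in the following circumstances". The list includes specified toxicities and this: "The subject experiences a clinically significant worsening of SLE warranting a significant change in therapy according to the Investigator".

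**Early termination.** The early-discontinuation visit is the Day 127 follow-up visit held early, and it collects every SRI component (protocol 4.3.3). SAP 6.4 labels its results as early termination and includes them in the summaries, without assigning them to a scheduled visit.

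**Endpoints.** SRI at Day 85 is the only secondary efficacy endpoint (protocol 6.2.3.2). It is derived from baseline and the visit alone (SAP 15.2.1.1), and is analysed and plotted at six visits (SAP 15.2.1, 15.2.1.2). Flares, active renal disease and corticosteroid use are analysed in the same way (SAP 15.3.8.2 to 15.3.12.2).

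**The concern.** Some of the reasons for withdrawal are themselves outcomes. A subject whose lupus worsens enough to need a significant change in therapy leaves the study, and then leaves the denominator of the response rate. The rate labelled FAS becomes a rate among those assessed at Day 85, plus perhaps those who missed that visit while still in the study. It is too high to the extent that leavers would not have responded. The per-protocol analysis offers no check, because it excludes the same subjects.

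A programmer also meets contradictory instructions. An in-study subject who misses Day 85 is a non-event under one sentence of SAP 15.1, is outside the denominator under the next, and may not be imputed under SAP 7.3 and protocol 8.2.2.

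Two related gaps follow from the same text:

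- **BICLA.** Protocol 6.2.2 makes premature discontinuation of study treatment a BICLA failure. SAP 15.3.2.1 derives BICLA for visits where all components are captured, which can be read as giving a withdrawn subject no Day 85 result. Its pointer for treatment failure goes to 15.3.15, which is SF-36; treatment failure is in 15.3.13.
- **Unfavourable events.** For SRI, a non-event is the cautious assumption. For a flare it is the favourable one: a missed visit becomes a flare-free visit.

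At stake is how the one secondary efficacy endpoint is read when a larger trial is designed (protocol 8.1).

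**Working it through.** **Inputs.** Four cohorts of 8 active and 2 placebo (protocol 4.1): 4 × (8 + 2) = 40 subjects, with 4 × 2 = 8 pooled placebo. This reproduces the planned enrolment. Each dose is compared with placebo by a two-sided Fisher exact test (SAP 15.2.1.2) at a nominal 5% (protocol 8.2). The documents give no power, response rate or withdrawal rate, so all counts and rates below are assumptions.

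**1. What each rule does with a subject who has no Day 85 assessment**

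| Rule | Still in study, missed Day 85 | Withdrawn before Day 85 |
|---|---|---|
| SAP 15.1, non-event sentence | non-responder | does not apply |
| SAP 15.1, denominator sentence | excluded | excluded |
| SAP 7.3, protocol 8.2.2 | not imputed | not imputed |
| FAS as all randomized (SAP 5.2) | in the set | in the set |

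**2. One arm of 8 under three readings.** Assume 4 responders, 2 observed non-responders, 1 in-study subject who missed Day 85 and 1 withdrawn. Wilson 95% intervals:

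- available data only: 4/6 = 66.7% (30.0 to 90.3)
- in-study miss counted as a non-event, withdrawn subject dropped: 4/7 = 57.1% (25.0 to 84.2)
- all randomized, missing counted as non-response: 4/8 = 50.0% (21.5 to 78.5)

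**3. Shift in the rate.** If w of 8 leave and all are non-responders, a rate p reads p / (1 − w/8). For p = 0.30 and w = 1, 2, 3: 0.30/0.875 = 0.343, 0.30/0.75 = 0.400, 0.30/0.625 = 0.480.

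**4. Shift in the test, in both directions**

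- One active non-responder dropped: 5/8 v 1/8, p = 0.119, becomes 5/7 v 1/8, p = 0.041.
- Two placebo non-responders dropped: 6/8 v 1/8, p = 0.041, becomes 6/8 v 1/6, p = 0.103.

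**5. How often the 5% verdict changes.** With w active non-responders removed, the active count runs from 0 to 8 − w and the placebo count from 0 to 8, giving (9 − w) × 9 tables.

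| w | Tables | Verdict changes | Gain p<0.05 | Lose p<0.05 |
|---|---|---|---|---|
| 1 | 72 | 4 | 4 | 0 |
| 2 | 63 | 7 | 4 | 3 |
| 3 | 54 | 9 | 5 | 4 |

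**6. Chance of p<0.05 with no true difference.** Exact enumeration of two binomials, n = 8 each; ranges are for true rates of 20% to 40%. With no leavers it is 0.4–1.9%.

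| Non-responding leavers | Active arm only | Same number in both arms |
|---|---|---|
| 1 | 1.5–4.5% | 0.4–1.9% |
| 2 | 1.5–5.1% | 0.4–1.8% |
| 3 | 5.6–10.0% | 2.6–4.8% |

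Only three of eight leaving the active arm and none leaving placebo, all non-responders, clearly exceeds 5%.

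**7. The alternative has its own bias.** Assume true rates of 60% v 20% and leaving unrelated to response. With no leavers the chance of p<0.05 is 24%.

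| Leavers | Active: as non-responders | Active: available data | Placebo: as non-responders | Placebo: available data |
|---|---|---|---|---|
| 1 | 13% | 31% | 27% | 27% |
| 2 | 5% | 19% | 31% | 20% |
| 3 | 1% | 25% | 35% | 15% |

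**The case against.** The strongest defence is that the SAP does what the protocol asks. Available-data percentages are in protocol 8.2 and no imputation is in protocol 8.2.2. A reader might infer that the denominator departs from the protocol; it does not. A reader might also infer that a withdrawn subject has no defined place in the analysis. The denominator sentence does place that subject, outside the rate. What is open is narrower: whether an early-termination assessment counts at Day 85. Counting leavers as non-responders is therefore a change to a protocol rule, not a correction of a SAP slip, and must be declared as one. All of this stands.

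Some of the conflict can be eased by letting specific rules govern general ones: 15.1 for efficacy over 7.3, and 15.3.7.1 for ACR. That does not settle the contradiction within 15.1, nor the fact that its non-event sentence is an undeclared exception to protocol 8.2.2.

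On BICLA, the SAP wording may mean visits at which the schedule collects all components, not a completeness test for each subject. It would then be too strong to say that a withdrawn subject certainly has no Day 85 result. The text allows both readings.

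On flares, SELENA and renal flares are recorded as occurrences on the eCRF, several SELENA criteria do not need that visit's assessment, and Kaplan-Meier analysis with censoring is planned. This offsets part of the concern.

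Finally, efficacy has no primary endpoint and no multiplicity control, time to treatment failure (SAP 15.3.13) already captures withdrawal for adverse events or lack of efficacy, and non-responder counting can cost more than it saves (step 7). These limit the severity; they do not tell a programmer which rule to apply.

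**Conclusion.** The point holds as a minor one. Read literally, the plan gives a Day 85 SRI rate that omits subjects withdrawn earlier while labelling it FAS. The per-protocol set repeats the omission, the status of early-termination data is unstated, and SAP 15.1 gives two answers for an in-study missed visit.

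The size depends on assumed withdrawals of one to three of eight. A 30% rate would read 34% to 48% if all leavers were non-responders. A subject who leaves for toxicity need not be a non-responder, so this is an upper case. Most tables do not cross 5%.

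A reader might infer that the rule favours the active drug or generally inflates false positives. The documents do not support that. The direction depends on which arm loses subjects, equal losses of non-responders in both arms keep the chance below 5% in the cases examined, and some tables lose significance. The estimate that informs the next trial is affected more than any formal conclusion.

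**What to change.** **SAP 15.1.** For SRI and the other favourable responder endpoints (BICLA, BILAG clinical and partial response, SLEDAI response, ACR), at every analysed visit, use all FAS subjects in the arm as the denominator. Count a subject with no assessment for that visit, including after withdrawal, as a non-responder. Applying this at Day 85 alone would mix denominators in the planned plot over study days. Keep the available-data result as a sensitivity analysis, for the reason shown in step 7. Leave the SRI definition unchanged.

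**Early termination.** State one rule for whether such an assessment counts at a scheduled visit, for example only if it falls in that visit's window (±2 days at Day 85). Show the alternative in the sensitivity analysis.

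**SAP 15.3.2.1.** State that treatment failure, including premature discontinuation of study treatment as in protocol 6.2.2, is BICLA non-response whether or not the visit's components were captured. Correct the pointer to 15.3.13.

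**Unfavourable events.** For SELENA, BILAG and renal flares, active renal disease and corticosteroid use, do not apply the non-event rule to missed visits. Report visit incidence among subjects observed, beside the planned Kaplan-Meier analysis.

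**Consistency.** Align SAP 6.1, 7.3 and 15.3.7.1, and declare the change from protocol 8.2 and 8.2.2 in SAP 3.4.

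**Cost.** Wording in these sections, a declared change to a protocol rule, and a sensitivity table for each responder endpoint. No extra data are needed. The choice should be fixed before unblinding.
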